**The risks of the Radioisotopes/radiation-producing machines (e.g., X-rays, CT scans, fluoroscopy) and associated risks.**

X-ray - x-ray involves exposure to an FDA-approved low dose of radiation. The radiation exposure from such x-rays is equivalent to that occurring from natural sources over two months, and increases the risk of cancer by 1/250,000.

**The risks of the Physical well-being.**

See above, Procedures to be performed.

**The risks of the Psychological well-being.**

A psychiatric screening will be performed to determine whether the participant meets inclusion and exclusion criteria for the study. From past experience, potential risk to participants is expected to be minimal. Specifically, questions asked may be potentially distressing to the participants or may cause them to think about problems relating to them that may be anxiety-provoking or upsetting. We have created and attached a suicidality protocol in the event that such a protocol is needed.

Cognitive Testing. There do not appear to be any risks associated with cognitive testing other than the commitment of significant time for participation. Some participants may experience anxiety during and after the cognitive testing.

Questionnaires. There are virtually no risks involved in filling out the questionnaires, sleep-wake cycle questionnaires and sleep logs other than the time involved.

MRI. One possible psychological risk is that some people experience claustrophobia during an MRI, or lesser degrees of anxiety.

**The risks of the Economic well-being.**

**Title :** Repetitive Transcranial Magnetic Stimulation to Improve Cognitive Function in TBI

**Approval Period:** 12/11/2018 - 02/13/2019

n/a

**The risks of the Social well-being.**

Loss of confidentiality

**Overall evaluation of Risk.**

Low - innocuous procedures such as phlebotomy, urine or stool collection, no therapeutic agent, or safe therapeutic agent such as the use of an FDA approved drug or device.

- b) If you are conducting international research, describe the qualifications/preparations that enable you to both estimate and minimize risks to participants. Also complete the International Research Form and attach it in the Attachments section. If not applicable, enter N/A.**

n/a

- c) Describe the planned procedures for protecting against and minimizing all potential risks. Include the means for monitoring to detect hazards to the participant (and/or to a potential fetus if applicable). Include steps to minimize risks to the confidentiality of identifiable information.**

- Loss of confidentiality.

o Every precaution will be taken to minimize loss of confidentiality. A double lock system will be maintained: within a locked office and locked file cabinet. All electronic data will be secured on an encrypted, password-protected database behind a VA firewall.

**MRI**

- There are no expected risks associated with the MR imaging of brain function, other than the possibility of some mild frustration and mild fatigue. The study participant may get a metal taste in their mouth or some tingling in their hands or feet during the MRI scan. Occasionally, individuals experience claustrophobia (fear of confinement in a small space) during the MRI scan.

o Breaks will be provided in order to reduce the possibility of frustration and fatigue.

o The metal taste sensations go away after the scan is complete.

o The MRI scanners have built-in communication systems, so study participants will have constant contact with staff during the scan. If the participant experiences severe claustrophobia, they will be asked to discontinue participation in the imaging measures in this study.

- Study personnel will verbally review the currently approved and required VA MRI scan checklist at the time of the telephone screen, and before every scheduled MR scan.

**rTMS**

In the unlikely event that a seizure does occur, the participant will be closely monitored and treated for any medical or psychological consequences. Lab tests will be drawn and the participant will be seen by a neurologist as soon as possible. The facility where the rTMS studies are performed is fully equipped to safely handle a seizure. The participant will be given a letter regarding the seizure to share with his or her primary health care provider. The letter will indicate that the seizure during rTMS does not increase risk for future seizures.

rTMS treatment can result in mild to moderate headaches in as many as 30 out of 100 of patients. Some people also report discomfort at the site of rTMS stimulation. This occurs in around 15 out of 100 of patients. Headaches and site discomfort usually readily respond to acetaminophen or ibuprofen. Painfulness improves over time or goes away. Often patients fall asleep in the second week while receiving the same treatment that on the first day was reported as very painful.

There is a small risk of dental pain with rTMS, during or immediately after the treatment. If this occurs, study staff may be able to move the rTMS coil position or provide a bite block to reduce this pain or make it not happen.

rTMS treatment may produce movement or tingling of the arm, leg, face or scalp. Participants may also experience a temporary feeling of numbness in the face.

**Title :** Repetitive Transcranial Magnetic Stimulation to Improve Cognitive Function in TBI  
**Approval Period:** 12/11/2018 - 02/13/2019

There is a possible risk of hearing loss due to the light clicking sounds made by the device. Participants will wear earphones during rTMS sessions. This should greatly reduce the possibility of hearing loss. Hearing will be tested at baseline, after the intervention phase, and after follow-up to see if any hearing loss has occurred.

The rTMS operator will monitor all participants for ear protection, coil placement, and seizure activity during all sessions.

- d) Explain the point at which the experiment will terminate. If appropriate, include the standards for the termination of the participation of the individual participant Also discuss plans for ensuring necessary medical or professional intervention in the event of adverse effects to the participants.**

The clinical trial will terminate after 2 years or when 40 participants have been through the protocol.

rTMS treatment will be done only by trained medical personnel (MD, Nurse, or Nurse Practitioner) who can provide necessary medical or professional intervention in the event of adverse effects to the participants.

- e) Data Safety and Monitoring Plan (DSMP). See guidance on Data Safety and Monitoring.**

**A Data and Safety Monitoring Plan (DSMP) is required for studies that present Medium or High risk to participants. (See Overall Evaluation of Risk above). If Low Risk, a DSMP may not be necessary. Multi-site Phase III clinical trials funded by NIH require the DSM Plan to have a Data Safety Monitoring Board or Committee (DSMC or DSMB). The FDA recommends that all multi-site clinical trials that involve interventions that have potential for greater than minimal risk to study participants also have a DSMB or DSMC.**

**The role of the DSMC or DSMB is to ensure the safety of participants by analyzing pooled data from all sites, and to oversee the validity and integrity of the data. Depending on the degree of risk and the complexity of the protocol, monitoring may be performed by an independent committee, a board (DSMC/DSMB), a sponsor's Data Safety Committee (DSC), a Medical Monitor, a sponsor's safety officer, or by the Protocol Director (PD).**

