**Rationale for the device being non-significant risk:**

After a decade of research, rTMS is generally regarded as safe and without lasting side effects if established guidelines are followed (Janicak et al., 2008; Machii et al., 2006). There have been no significant cognitive (Triggs et al., 1999; Little et al., 2000), neurological (Nahas et al., 2000) or cardiovascular sequelae reported as a result of rTMS. See answer to 9 A.

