**The risks of the Investigational drugs. Information about risks can often be found in the Investigator's brochure.**

n/a

**The risks of the Commercially available drugs, reagents or chemicals. Information about risks can often be found in the package insert.**

n/a

**The risks of the Procedures to be performed. Include all investigational, non-investigational and non-invasive procedures (e.g., surgery, blood draws, treadmill tests).**

rTMS - rTMS Safety especially for Mild and Moderate TBI Veterans

After a decade of research, rTMS is generally regarded as safe and without lasting side effects if established guidelines are followed (Janicak et al., 2008; Machii et al., 2006). There have been no significant cognitive (Triggs et al., 1999; Little et al., 2000), neurological (Nahas et al., 2000) or cardiovascular sequelae reported as a result of rTMS.

The primary safety concern with rTMS, in any population, has been the risk of seizure induction. Eight seizures have been reported secondary to rTMS (Wassermann, 1998). These have occurred in a sample size estimated to be over several thousand rTMS treatment sessions. The rTMS community has adopted and widely used the guidelines prescribing a safe interval between pulse trains (Gerloff et al., 1997) and the safety guidelines from a National Institute of Neurological Disorders and Stroke (NINDS) workshop on rTMS. To our knowledge there have been two publications since 1997 describing events during rTMS that might be considered seizures. Conca and colleagues reported a patient who experienced a 'pseudoabsence seizure'. It is unclear if this was a true seizure (Conca et al., 2000). Bernabeu and colleagues reported on a patient who had a seizure during rTMS. In this case, there was a brief interstimulus interval (Bernabeu et al., 2004). The risk of seizures for rTMS treatment is less than 1%.

How does this impact our study: The current safety guidelines have not been tested for mild and moderate TBI population which is precisely the purpose of this pilot grant. In TBI population, posttraumatic epilepsy

**Title :** Repetitive Transcranial Magnetic Stimulation to Improve Cognitive Function in TBI  
**Approval Period:** 12/11/2018 - 02/13/2019

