is the most common delayed sequelae of TBI. But this incidence is very low (about 5%) in TBI patients with closed head injury (Ropper et al., 2005) who are most likely our mild and moderate TBI patients. In a clinical setting, for example in Polytrauma Transitional Rehabilitation Program (PTRP – VAPA) the expected recovery trajectory for persons with mTBI is full cognitive recovery in 3-6 months following injury. Persisting or worsening cognitive status is often related to other co-morbid psychiatric issues, such as depression and PTSD, chronic pain, sleep apnea (all will be) used as covariates in our analysis). Including persons with moderate TBI in our study would likely allow for examination of rehabilitation treatment effects on cognitive functioning for those who tend to have persisting cognitive difficulties following injury. On PTRP, patients are often admitted from the acute inpatient rehab unit on anticonvulsant medications if they had a seizure 1 day or more following the injury. Typically, if the patient experienced a seizure immediately at the scene of the incident, they are not considered at a greater risk for subsequent seizures. For those who do not have a history of seizures following injury, they are not considered at a greater risk of subsequent seizures and are not placed on anticonvulsant medications. Importantly, the interval between the head injury and the first seizure varies greatly (Demirtas-Tatlidede et al., 2012) and must be considered as a variable for recruitment in this study. Currently PTRP houses patients 2 months to 2 years post TBI. Note, that there is only one case study which performed detailed safety assessments and reported a lack of adverse events in a patient with severe TBI following application of a specific rTMS protocol over 5 consecutive days through 6 weeks (Pape et al., 2009). Our protocol will be highly stringent and will exclude any severe TBI patients (including those with any fractures, metal plates or open head injuries), acute patients or those who have had a concussion within the last 2 months, and those who have a history of seizures of any type.

Neuropsychology testing - The risks posed by neuropsychological testing are mild frustration and mild fatigue that will not persist.

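### Section 9c fixes in advance, with no condition or source, that the letter given after a seizure will say future seizure risk is not increased

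*Protocol*

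**What the plan says.** The rTMS paragraph of section 9c sets out the response to a seizure. The participant is monitored and treated, blood is taken for lab tests, and "the participant will be seen by a neurologist as soon as possible". The participant then receives a letter to pass on to the primary care provider. Its message is given in one sentence: "The letter will indicate that the seizure during rTMS does not increase risk for future seizures".

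The safety background is elsewhere:

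- Section 5.1 (rationale for non-significant risk) and section 9a (risks of the procedures) describe general experience: "rTMS is generally regarded as safe and without lasting side effects if established guidelines are followed". They add that no significant cognitive, neurological "or cardiovascular sequelae reported as a result of rTMS".
- Section 9a reports eight seizures secondary to rTMS and two later publications, and puts the risk below 1%.
- Section 9a then says of the study population: "The current safety guidelines have not been tested for mild and moderate TBI population".
- Section 9a also puts post-traumatic epilepsy at about 5% in closed head injury and says the time from injury to first seizure varies greatly.

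Section 8h excludes people with any prior seizure and those injured within the last two months. Section 16 lists two attachments, Seizure Protocol and safety_Protocol, whose text is not shown.

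**The concern.** The letter's conclusion is set before the event has been assessed. As written, the same assurance goes out whatever the lab tests or the neurologist find. The paragraph does not separate a seizure plausibly provoked by stimulation from one that happened to occur during a session, and it makes no exception for sham participants, in whom active stimulation cannot be the cause.

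The person meant to read the letter is the clinician who decides on further work-up after the study visit. A categorical statement that risk is not raised could discourage follow-up that a first post-traumatic seizure would call for. What is at stake is participant safety and the accuracy of what participants are told. No endpoint, estimate or test depends on it.

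**Working it through.** The check is mainly textual: does anything in the protocol support the assurance for these participants, and does anything make it conditional?

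**1. Conditions.** Section 9c has the letter given and has it carry the message, both without qualification. Lab tests and the neurologist visit are in the same paragraph, but the letter's wording does not depend on their results. The paragraph does not refer to the attachments.

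**2. Source.** The sentence has no citation. Sections 5.1 and 9a give general safety statements, but the protocol never links them to the letter. They are background at most.

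**3. Recurrence data.** Each seizure figure in the protocol is about occurrence:

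| Figure (section 9a) | What it measures |
|---|---|
| Eight seizures, plus two later reports | Seizures occurring under rTMS; no recurrence outcome given |
| Below 1% | Risk of a seizure with rTMS, not specific to TBI |
| About 5% | Post-traumatic epilepsy in closed head injury |
| One severe-TBI case without adverse events | No seizure to follow up |

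None of these yields a risk of a further seizure after an rTMS seizure, in TBI or in any other population.

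**4. Could the seizure have another cause?** Under section 8h, a seizure on study would be the first known one, at least two months after injury. Section 9a acknowledges that a first post-traumatic seizure can come at very variable times. It follows from the protocol's own account that a seizure during a session could be a first post-traumatic seizure, in either arm. How likely that is cannot be derived: the 5% is an overall incidence with no time base and cannot be converted into a probability for a treatment course of 2 to 6 weeks.

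**5. How often the letter might be needed.** Inputs: the general risk below 1% (section 9a), read here as per person because no unit is given; 40 participants (section 9d) or 100 (section 8a); 1:1 allocation, which is assumed because the ratio is not stated.

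- 40 participants, 20 active: expected letters below 0.01 × 20 = 0.2; chance of at least one below 1 − 0.99^20 = 18.2%.
- 100 participants, 50 active: expected letters below 0.01 × 50 = 0.5; chance of at least one below 1 − 0.99^50 = 39.5%.

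These are ceilings under a general rTMS rate. They are not estimates for mild or moderate TBI, and they leave out sham participants and seizures unrelated to stimulation. They show that the event is uncommon and do not determine the severity of the point.

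**The case against.** The strongest reply is that no error has been shown. The sentence can be read narrowly: the seizure provoked by stimulation adds no risk of its own. On that reading it does not deny an underlying risk of post-traumatic epilepsy and does not conflict with section 9a. The statement about untested guidelines follows a discussion of seizures induced by stimulation and does not address recurrence. Clinical oversight is also substantial. A neurologist sees the participant promptly, and under section 9e the monitoring group includes neurologists with rTMS and TBI expertise, meets for every patient and receives serious adverse events within 48 hours. Nothing stops the letter from saying more, and the attachments may already make it conditional.

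Most of this stands. The sentence may be true, and the safeguards lower the chance of harm. They do not change what the letter is required to say. The narrow reading takes for granted that stimulation caused the seizure, which is the question the neurologist is there to answer.

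Two stronger readings are tempting, and the documents support neither. A reader might infer that the assurance is false. The protocol has no recurrence data in either direction, so that cannot be concluded. A reader might also infer that section 9a contradicts section 9c, because its reassurance covers only two groups: "if the patient experienced a seizure immediately at the scene of the incident, they are not considered at a greater risk for subsequent seizures", and "For those who do not have a history of seizures following injury, they are not considered at a greater risk of subsequent seizures". A participant who has just had a seizure on study would fit neither. Those sentences, however, describe how a rehabilitation programme regards seizures in relation to the injury. They were not written to cover seizures provoked by stimulation and are not offered in support of the letter, so falling outside both groups proves nothing about it.

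**Conclusion.** The point holds as a badly fixed rule. Section 9c commits the study to a categorical statement about future seizure risk, with no condition and no source, when the protocol has no recurrence data and itself leaves room for a first post-traumatic seizure during a session. It is minor: the event is rare, specialist review is already planned, and endpoints and analysis are untouched.

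The conclusion rests on the text of section 9c alone. If the Seizure Protocol or safety_Protocol attachment already makes the letter subject to the neurologist's findings, all that remains is to bring section 9c into line with it. The frequency ceilings rest on the per-person reading of the below-1% figure and on the assumed 1:1 allocation; the textual point needs neither.

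**What to change.** Replace the sentence in section 9c with: *The letter will report the seizure and the treatment circumstances and give the neurologist's individual assessment of its likely cause, future seizure risk and any recommended follow-up.* Change the template letter and, if needed, the two attachments to match.

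The replacement should not go on to say that risk after an rTMS seizure is unestablished in mild or moderate TBI. That would be a claim about the wider literature, which the protocol does not make; it says only that the safety guidelines are untested in this group.

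The cost is one sentence and a template edit, using a neurologist visit that is already planned. The downside is that the letter is less categorically reassuring to the participant and cannot be issued until the neurologist's assessment is available.

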**d) Sufficient time.**

**Explain whether you will have sufficient time to conduct and complete the research. Include how much time is required.**

This project is expected to last for 2 years. The duration of the study will be two years, with 18 month enrollment period, and the last six months will be strictly for follow-up. 20 participants will be recruited in the first year and 20 will be recruited in the second year. Each participant will be in the trial for a total of approximately 28 weeks (1-2 weeks screening, 2 weeks acute treatment phase (depending on scheduling constraints) and a follow-up visit at 26 weeks post-treatment. The last 6-8 months of the study will also be spent analyzing data and writing up results.

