## 1. Purpose

**a) In layperson's language state the purpose of the study in 3-5 sentences.**

Repetitive Transcranial Magnetic Stimulation (rTMS) to Improve Cognitive Function in TBI: The proposed study will evaluate the safety, durability and efficacy of repetitive Transcranial Magnetic Stimulation (rTMS) as a promising non- invasive therapeutic treatment for executive function (EF) deficits and other outcomes (such as: headache, pain, etc) seen in 100 Veterans with mild to moderate Traumatic Brain Injury (TBI).

**b) State what the Investigator(s) hope to learn from the study. Include an assessment of the importance of this new knowledge.**

Many returning OEF/OIF Veterans with concussion histories report cognitive problems that may last for months or even years (Schneiderman et al., 2008; Hoge et al., 2008). Although deployment itself can be associated with cognitive problems (Vasterling et al, 2006), having co-morbid conditions such as post traumatic stress disorder (PTSD) and depression may prolong the symptoms of TBI resulting in lowered attention, processing speed, learning and memory (Nelson et al., 2012; Caeyenberghs et al., 2012). Strong evidence also suggests that a history of TBI increases risk for developing PTSD (Eckart et al., 2011). Significant progress has been made towards understanding the pathophysiology and neuropsychological changes associated with the acute and long term sequelae of TBI, including its complicated relationship with PTSD (Brenner et al., 2011; Hallbauer et al.,

---

**Title :** Repetitive Transcranial Magnetic Stimulation to Improve Cognitive Function in TBI  
**Approval Period:** 12/11/2018 - 02/13/2019

---

2009;  
Villamar et al., 2012). However, few studies have addressed what mechanisms of TBI may be responsive to therapeutic treatment.

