## 8. Participant Population

- a) **State the following: (i) the number of participants expected to be enrolled at Stanford-affiliated site(s); (ii) the total number of participants expected to enroll at all sites; (iii) the type of participants (i.e. students, patients with certain cancer, patients with certain cardiac condition) and the reasons for using such participants.**

(i) 100 participants are expected to be enrolled  
(ii) 100 participants at VAPAHCS  
(iii) all participants will be Veterans, Military personnel and Civilians.

- b) **State the age range, gender, and ethnic background of the participant population being recruited.**

Age range: 20-65 years  
Note: We may include participants between 65-70 if they contact us and pass the screening (and are not showing cognitive decline related to dementia)  
Gender: Males and Females  
Ethnic Background: Any race or ethnic origin

- c) **State the number and rationale for involvement of potentially vulnerable subjects in the study (including children, pregnant women, economically and educationally disadvantaged, decisionally impaired, homeless people, employees and students). Specify the measures being taken to minimize the risks and the chance of harm to the potentially vulnerable subjects and the additional safeguards that have been included in the protocol to protect their rights and welfare.**

Children, pregnant women, economically and educationally disadvantaged, decisionally impaired, and homeless people will not be recruited for this protocol.

- d) **If women, minorities, or children are not included, a clear compelling rationale must be provided (e.g., disease does not occur in children, drug or device would interfere with normal growth and development, etc.).**

There will be no participation of children in this study.

- e) **State the number, if any, of participants who are laboratory personnel, employees, and/or students. They should render the same written informed consent. If payment is allowed, they should also receive it. Please see Stanford University policy.**

It is unlikely that any laboratory personnel, employees, or students will qualify for participation in this study. If any do qualify and wish to participate, they will be treated the same as any other participant.

**Title :** Repetitive Transcranial Magnetic Stimulation to Improve Cognitive Function in TBI  
**Approval Period:** 12/11/2018 - 02/13/2019

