- f) **State the number, if any, of participants who are healthy volunteers. Provide rationale for the inclusion of healthy volunteers in this study. Specify any risks to which participants may possibly be exposed. Specify the measures being taken to minimize the risks and the chance of harm to the volunteers and the additional safeguards that have been included in the protocol to protect their rights and welfare.**

Participants should all be in fair physical health though may be cognitively impaired as seen in the chronic symptoms of mild/moderate TBI (note we have removed the 1 SD or more below the mean score on Trail Making Test B (TMT B) criteria from our inclusion criteria). All procedures are considered low risk or standard of care.

- g) **How will you identify participants for recruitment? (E.g., by: chart review; referral from treating physician; response to ad). Attach recruitment materials in Section #16 (Attachments). All Final or revised recruitment materials, flyers, etc. must be submitted to the IRB for review and approval before use. You may not contact potential participants prior to IRB approval. See Advertisements: Appropriate Language for Recruitment Material.**

Based on the team established, we will recruit from: War Related Illness and Injury study Center (WRIISC) at VAPA (one of the three in the nation tasked to address complex problems faced by Veterans of the recent wars; PI: [name], PhD, Deputy Director Research), Polytrauma VAPA (Co-I: [name]; one of the 5 polytrauma network sites the country and a participating DVBIC site), Memory clinics at VAPA as well as from the surrounding VA clinics. Letters will be sent to patients and providers with information about the study, and a pre-paid response postcard. Phone calls will be made to these Veterans as followup within two weeks. Flyers will be posted in relevant clinic settings and on the Stanford University Marguerite Shuttle, and study information will be advertised on social media, including facebook. (We plan to recruit an average of 2.2 patients/month to meet our target enrollment of 40 participants in 18 months).

- h) **Inclusion and Exclusion Criteria.**

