**Identify exclusion criteria.**

**Exclusion Criteria**

- Pregnant or lactating female.
- Unable to be safely withdrawn, at least two-weeks prior to treatment commencement, from medications that substantially increase the risk of having seizures
- Have a cardiac pacemaker or a cochlear implant
- Have an implanted device (deep brain stimulation) or metal in the brain (see standard MRI exclusion criteria including metal screening section in telephone screen, Appendix A).
- Have a mass lesion, cerebral infarct or other active CNS disease, including a seizure disorder.
- Known current psychosis as determined by DSM-IV coding in chart (Axis I, psychotic disorder, schizophrenia) or a history of a non-mood psychotic disorder.
- Diagnosis of Bipolar Affective Disorder I (as determined by chart review and intake interview)
- Current amnesic disorders, dementia, MOCA ≤ 16, or delirium.
- Current substance abuse (not including caffeine or nicotine) as determined by positive toxicology screen, or by history via AUDIT, within 3 months prior to screening
- Prior history of seizures

**Title :** Repetitive Transcranial Magnetic Stimulation to Improve Cognitive Function in TBI  
**Approval Period:** 12/11/2018 - 02/13/2019

- Severe TBI or open head injury
- TBI within last two months or in acute stage
- Participation in another concurrent clinical trial
- Patients with prior exposure to rTMS (NOTE: TMS is allowed)
- Active current suicidal intent or plan. Patient at risk for suicide will be required to establish a written safety plan involving their primary psychiatrist and the treatment team before entering the clinical trial

**i) Describe your screening procedures, including how qualifying laboratory values will be obtained. If you are collecting personal health information prior to enrollment (e.g., telephone screening), please request a waiver of authorization for recruitment (in section 15).**

Research Assistants will assess for participant eligibility in a telephone screen. Telephone screening will assess a potential participant's background, demographics, health questions, and psychiatric stability. Study Personnel will meet once per week to review, discuss, and make determinations about the appropriateness of potential participants for the study.

If by study midpoint (approximately end of year one) we are unable to get 20 participants per year, we will reconsider inclusion/exclusion criteria.

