**l) Costs. Please explain any costs that will be charged to the participant.**

**Title :** Repetitive Transcranial Magnetic Stimulation to Improve Cognitive Function in TBI  
**Approval Period:** 12/11/2018 - 02/13/2019

There are no costs to participants other than time and inconvenience.

**m) Estimate the probable duration of the entire study. Also estimate the total time per participant for: (i) screening of participant; (ii) active participation in study; (iii) analysis of participant data.**

Duration of the study: 2 years

Total time per participant for all screening: 7-8 hours.

For active participation in the study -

- Baseline: approximately 8 hours on-site with MRI, labs, clinical exams
- Intervention: approx. 30-60 minutes/session, 20 sessions over 2 -6 weeks, depending on scheduling
- Follow-up: one follow-up visits over 6 months, each visit lasting approx. 8.5 hrs

Analysis of participant data immediately post treatment and at 6 month follow-up

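### The protocol gives two incompatible sample sizes, 100 in sections 1a and 8a and 40 in Resources (d), 8g and 9d, and its recruitment plan and termination rule cannot deliver 100

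*Protocol*

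**What the plan says.** Two sections give 100. Section 1a describes the deficits to be treated as those "seen in 100 Veterans with mild to moderate Traumatic Brain Injury (TBI"). Section 8a(i) says "100 participants are expected to be enrolled", and 8a(ii) gives the same number for all sites together, all at VAPAHCS. The General Checklist says the study is not multi-site.

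The operational sections give 40:

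- Resources (d), yearly split: "20 participants will be recruited in the first year and 20 will be recruited in the second year".
- Resources (d), timetable: two years, "with 18 month enrollment period, and the last six months will be strictly for follow-up".
- Section 8g: "We plan to recruit an average of 2.2 patients/month to meet our target enrollment of 40 participants in 18 months".
- Section 9d: "The clinical trial will terminate after 2 years or when 40 participants have been through the protocol".

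Two further places depend on the same timetable. Section 8i sets a check at about the end of year one: if "we are unable to get 20 participants per year, we will reconsider inclusion/exclusion criteria". Section 8m says "Duration of the study: 2 years".

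**The concern.** One quantity, the number of people to be enrolled at one site, has two values that differ by a factor of 2.5. Both stand in current text. The population section uses one value, while the recruitment target and the rule that ends the trial use the other.

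What is at stake is when recruitment stops. Staff who follow 9d and close at 40 leave the trial 60 short of 8a. Staff who continue to 100 go past the point at which 9d says the trial is over. Neither course complies with the whole document. Any later statement about whether the trial reached its planned size would depend on which section the reader takes as the plan.

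**Working it through.** **Inputs**

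- Enrolment of 100: sections 1a, 8a(i) and 8a(ii).
- Recruitment of 20 + 20: Resources (d).
- Average of 2.2 per month for 18 months, target 40: section 8g.
- Enrolment window of 18 months, study of 24 months: Resources (d) and 8m.
- Time in trial of about 28 weeks per participant, or about 6.4 months: Resources (d).
- Termination at 2 years or 40 participants: section 9d.

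**Step 1. Reproduce 40.** Number enrolled = rate × months.

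- 2.2 × 18 = 39.6, which rounds to 40. In reverse, 40 / 18 = 2.22 per month.
- 20 + 20 = 40.

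The stated rate, window and yearly totals all return 40.

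**Step 2. Try to reproduce 100.**

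- Over the 18-month window: 2.2 × 18 = 39.6.
- Over all 24 months, ignoring the follow-up-only period: 2.2 × 24 = 52.8.

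No stated rate and window return 100.

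**Step 3. What 100 would require.**

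- In 18 months: 100 / 18 = 5.6 per month, about 2.5 times the stated rate.
- In 24 months: 100 / 24 = 4.2 per month, about 1.9 times the stated rate.
- At the stated rate: 100 / 2.2 = 45.5 months, against a window of 18 and a study of 24.

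**Step 4. Apply the termination rule in 9d.**

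- Two-year limb: at 2.2 per month no more than 52.8 have entered by month 24.
- 40-participant limb, counting entries: the trial ends at 40.
- 40-participant limb, counting completers: entries when the 40th completes = 40 + rate × time in trial. At 2.2 per month this is 40 + 2.2 × 6.4 = 54. Even at the 5.6 per month that 100 would need, it is 40 + 5.6 × 6.4 = 76.

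All of these fall short of 100.

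**Step 5. Do the 40-based statements agree with each other?**

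- Year one: 20 / 12 = 1.67 per month.
- Months 13 to 18: 20 / 6 = 3.33 per month.
- Average over the window: (20 + 20) / 18 = 2.22 per month.

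They agree if recruitment is faster in the last six months of the window.

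**The case against.** **Readings that might remove the conflict.** One could take 100 as the number enrolled and 40 as the number completing. The wording does not allow it: 8g attaches 40 to enrolment and Resources (d) attaches its 20 + 20 to recruitment, while 8a attaches 100 to enrolment. One could take 100 as a ceiling, but 8a presents it as the expected number and 1a as the number to be studied. Different sites cannot explain it, since 8a gives 100 both for the affiliated site and in total. A sample-size rationale may sit in an attachment that is not shown, such as the grant listed in section 16. That would not change the fact that the sections of this protocol disagree.

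**Stronger readings that the documents do not support.**

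- *That the 40-based plan contradicts itself.* A reader might infer this because a constant 2.2 per month gives about 26 by month 12, not 20, and because 20 per year held constant gives 30 by month 18. But 8g states an average, not a constant rate, and Step 5 shows that 20 and then 20 satisfies it. The check at 20 in 8i is the year-one plan itself. A constant pace would be the reader's assumption.
- *That one of the numbers is statistically inadequate.* The standard error of an active-sham difference would be √(100/40) = 1.58 times larger at 40 than at 100, assuming equal arms, equal SD and no dropout. This is scaling only. The protocol calls the study a pilot and links neither number to a power calculation.
- *That the target was raised from 40 to 100 during the study, perhaps after results were seen.* The modification summary carries 100 in its wording for 1a and 8a, but the underlining that marked the new words is lost. It cannot be told whether the number was among the changes, and nothing suggests that results by arm prompted one.
- *That 9d cuts off the last participant's six-month visit.* Its 40-participant limb reads naturally as including that visit, because Resources (d) counts the 26-week follow-up in each participant's time in the trial.

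What stands of the case against is that the sums behind 40 are correct. The defect is an inconsistency between sections, not a miscalculation.

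**Conclusion.** The point holds as an internal inconsistency and must be resolved, because one of the two numbers also ends the trial. The gap is 60 participants. The stated plan produces 40, and at the stated rate it could not produce more than about 53 within the stated two years. The shortfall figures rest only on the rate, window and duration in the protocol. The completer reading in Step 4 also assumes about 6.4 months in the trial for each participant and a constant rate. The conflict itself needs no assumption, since the two numbers stand in plain terms for the same quantity. The protocol does not contain what would be needed to say which number is right, and this review does not say so.

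**What to change.** State one target number in sections 1a, 8a, 8g, 9d and Resources (d), and say in 9d whether it counts enrolled, randomized or completed participants.

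- **If 40 is intended:** correct 1a and 8a and clarify the count in 9d. The rate, yearly split, window and midpoint check can stay. The cost is wording only.
- **If 100 is intended:** correct the recruitment rate (8g), the yearly split and enrolment window (Resources (d)), the midpoint check (8i), the study duration (Resources (d) and 8m) and both limbs of the termination rule (9d) so that they agree with 100. Besides the wording, this costs a higher rate that the site can defend, a longer study, or both. The figures in Step 3 show the size of the change.
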